8.6 Limitations of the Study

All patients will be required to meet the inclusion/exclusion criteria specified in this document, which may limit the overall range of patients to which inferences may be applied. Additionally, this study is not designed to provide data beyond 2 years after filter placement or beyond 1 month after filter retrieval.

9.0 Deviations from Clinical Investigation Plan

Investigators are not allowed to deviate from this CIP without prior authorization by the sponsor except under emergency situations when necessary to preserve the rights, safety, or well-being of study patients.

Deviations (failures to follow requirements of the CIP) and noncompliances (failures to follow applicable regulations) will be recorded together with an explanation. Deviations or noncompliances that impact the rights, welfare, or safety of patients shall be promptly reported to the sponsor and IRB/EC/REB as required.

If appropriate, corrective and preventive actions will be discussed by the sponsor, investigator, and/or the IRB/EC/REB to determine a suitable course of action.

10.0 Data Collection and Reporting

10.1 Electronic Case Report Forms

Patient data will be collected and entered by trained personnel at the clinical site onto electronic Case Report Forms (eCRFs) through an Electronic Data Capturing (EDC) system. This is a secure, web-based system, allowing those with permission to access

data from any location at any time. Source data are to be retained for data entered into the eCRF system. Data obtained and simultaneously entered into the EDC system may also serve as source documentation. Worksheets created from the eCRF are available to each site and may serve as source documentation (e.g., 18-month telephone follow-up). Site personnel are required to undergo data entry training and will have unique login names and passwords in order to enter patient data. In accordance with 21 CFR Part 11, the eCRF system creates a secure, computer-generated, time stamped audit trail to record the date and time of operator entries and actions that create, modify, or delete electronic records.

10.2 Data Reporting

Progress reports will be submitted to FDA every 6 months for the first 2 years of the study and annually thereafter, from the date that this CIP is approved by FDA. A final report will be submitted to FDA no later than three months after study completion (i.e., after the last patient completes their last follow-up visit). In the event the study is terminated prior to completion, a final report will be submitted to FDA no later than three months after study termination.

Also, as required by local regulations, progress reports and a final report at the conclusion of the clinical study will be submitted by the investigators and sponsor to the regulatory authorities and/or IRB/EC/REB.

11.0 Data Management and Quality Assurance

11.1 Data Entry and Quality Assurance

Each principal investigator or appropriately trained designee shall enter the clinical data into the electronic data capture system on standardized CRFs. Investigators will provide all applicable clinical data and documentation to the sponsor. Patient data and documents pertaining to the study will be kept and archived by the sponsor. Data will be reviewed for missing data, data consistency, and reasonableness of responses. Discrepancies will be resolved through a formal query process involving direct contact with investigators or research coordinators. The data coordinating center is responsible for database management, data verification, data archiving, and data retention.

As needed to assist the sponsor in its research (e.g., during evaluation of an adverse event), data will be accessible to the sponsor, the participating investigators, the manufacturer, and companies or individuals the sponsor authorizes.

11.2 Data Monitoring Arrangements

The conduct of the clinical study will be supervised through a process of remote and on-site monitoring. The data coordinating center will remotely monitor the study for data completeness and for adverse events. On-site monitoring will be implemented as necessary throughout the course of the study. The investigator/institution will provide direct access to source data/documents for study-related monitoring, audits, IRB/EC/REB review, and regulatory inspection. Written procedures for monitoring the study are maintained by the data coordinating center and are summarized in Appendix B.

12.0 Safety Monitoring and Procedures for Reporting Adverse Events

12.1 Safety Monitoring

An independent Clinical Events Committee (CEC) consisting of physicians, who are not investigators in the study and who do not have a perceived conflict of interest with the conduct and administration of the study, will be established to adjudicate clinical events reported during the study. This adjudication will be performed to assess whether the events were due to a pre-existing or unrelated condition, or were procedure-related, technique-related, and/or device-related.

A central core laboratory will be used for image analysis to provide uniformly defined analysis of images.

Regularly scheduled reviewing/monitoring of all patient data will be conducted at the data coordinating center, in part, for identification of adverse events and assurance that they are correctly reported to the CEC.

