6.3.2 Primary Safety Endpoint

The primary safety endpoint is the rate of 12-month freedom from major adverse events. Major adverse events are defined as: clinical perforation, clinical migration, clinical fracture, embolization of the filter or filter fragments to the heart or lungs, IVC thrombotic occlusion, new symptomatic DVT while a filter is indwelling, access site complications with clinical sequelae, and procedure-/device-related death. Analysis of the primary safety endpoint will be performed separately for each filter type (i.e., each stratum).

Events occurring after filter retrieval (i.e., through the 1-month post-retrieval follow-up period) will be collected, but only the events of access site complications with clinical sequelae and procedure-related death will count against the primary safety endpoint. Other events (i.e., potentially new DVT without symptoms) will be reported as a secondary measure.

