6.3.3 Secondary Endpoints

The secondary endpoints include:

- Rate of technical placement success and 12-month freedom from new symptomatic PE while a filter is indwelling for the combined patient population
- Rate of 12-month freedom from major adverse events for the combined patient population

- Rate of 12-month freedom from Grade 2 or Grade 3 filter leg interaction with the IVC, filter migration, filter fracture, and filter embolization for both the individual stratum and the combined patient population

All primary and secondary endpoints will also be reported at 24 months. In addition, analysis of the following secondary measures will be performed separately for each filter type (i.e., each stratum) and for the combined patient population:

- Filter leg interaction with the IVC wall
- Clinical perforation
- Migration > 2 cm (including direction)
- Symptomatic PE (occurring before and after filter retrieval)
- PE (occurring before and after filter retrieval)
- IVC thrombotic occlusion (occurring before and after filter retrieval)
- Symptomatic DVT (occurring before and after filter retrieval)
- DVT (total incidence and new incidence; occurring before and after filter retrieval)
- Retroperitoneal hematoma
- Hematoma at access site
- Infection at access site
- Thrombosis at access site
- Death
- Filter tilt (with measurement)
- Filter fracture
- Filter embolization
- Filter deformation
- Length of procedure (insertion and retrieval)
- Length of ICU stay
- Length of hospital stay
- Technical placement success
- Filter retrieval attempts
- Technical retrieval success
- Failed retrieval attempts, with reason for failed attempt
- Retrieval-related complications
- Adverse events occurring after filter retrieval
- Delivery system performance

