8.1.2 Primary Safety Hypothesis

The primary safety endpoint is the rate of 12-month freedom from major adverse events. Major adverse events are defined as: clinical perforation, clinical migration, clinical fracture, embolization of the filter or filter fragments to the heart or lungs, IVC thrombotic occlusion, new symptomatic DVT while a filter is indwelling, access site complications with clinical sequelae, and procedure-/device-related death. The analysis requires that the performance goal of 80% be met for freedom from major adverse events at 12 months. The performance goal was derived based on what are considered clinically acceptable rates for each complication in the overall population.⁴⁸

The null (H_0) and alternative (H_A) hypotheses are expressed as follows:

$$H_0: S(t) \leq 80\%$$

$$H_a: S(t) > 80\%$$

where:

- t is time through 12 months
- $S(t)$ is the true rate of freedom from major adverse events at time t .

The hypothesis will be assessed using a Z-statistic. The Z-statistic is given by

$$Z = (\hat{S}(t) - 0.8)/SE$$

where:

- $\hat{S}(t)$ = Kaplan-Meier estimate of freedom from major adverse events ($S(t)$) at 12 months
- SE = Standard Error = $\sqrt{V(S(t))}$, where $\hat{V}(\hat{S}(t))$ is the estimate of the variance of the Kaplan-Meier estimate using the methods described by Peto et al.⁵⁰

The performance goal will be said to have been met provided the null hypothesis is rejected in favor of the alternative if $\hat{S}(t) - 0.8 > Z_{\alpha}SE$, for $\alpha = 0.025$. The hypothesis will be tested only for patients receiving Celect[®] filters.

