8.3 Sample Size

The study is designed to enroll 320 patients in the Celect[®] filter stratum (to evaluate the safety and effectiveness hypotheses) and up to 150 patients in the Günther Tulip[®] filter stratum at up to 40 sites globally. At least half of the study patients in the Celect[®] filter stratum will be enrolled at US sites.

For the primary effectiveness endpoint, based on what are considered clinically acceptable rates for technical placement success and new symptomatic PE in the overall

population, a performance goal of the rate of technical placement success and 12-month freedom from new symptomatic PE while a filter is indwelling was established to be 90%.⁴⁸ Additionally, based on the data from previous Cook sponsored studies (as summarized in Section 4.0), the rate of technical placement success and 12-month freedom from new symptomatic PE while a filter was indwelling was estimated to be 98.4% for the Celect[®] filter stratum. A sample size of 70 patients will be required to assess the primary effectiveness hypothesis for the Celect[®] filter stratum, with a one-sided exact binomial test, at a type I error rate of 0.025, and a power of 0.9. The calculation was performed with the SAS UnifyPow macro.

For the primary safety endpoint, based on what are considered clinically acceptable rates for each complication in the overall population, a performance goal of the rate of 12-month freedom from major adverse events was established to be 80%.⁴⁸ Based on the data from previous Cook-sponsored studies (as summarized in Section 4.0), the rate of 12-month freedom from major adverse events was estimated to be 92.2% for the Celect[®] filter stratum. A sample size of 88 patients will be required to assess the primary safety hypothesis for the Celect[®] filter stratum, with a one-sided exact binomial test, at a type I error rate of 0.025, and a power of 0.9. The calculation was performed with the SAS UnifyPow macro.

Based on sample size calculations, a minimum of 88 patients in the Celect[®] filter stratum will be required to evaluate the safety and effectiveness endpoints. Cook intends to enroll 320 patients in the Celect[®] filter stratum; this sample size allows for an attrition rate of 72% (i.e., 60% of filters to be retrieved prior to 12 months and an additional 12% of patients who may die, withdraw, or become lost to follow-up). The study may also enroll up to 150 patients in the Günther Tulip[®] filter stratum.

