- Grade 2: Filter strut is entirely outside of the IVC lumen and within the retroperitoneum as evidenced by a “halo” of retroperitoneal fat around axially viewed strut.
- Grade 3: Filter strut is touching, impressing, or perforating another organ (e.g., liver, bowel, aorta, psoas muscle, vertebral body, lymph nodes).

Filter migration – Change in filter position compared to its deployed position (cranial or caudal). Migration will be classified as significant (i.e., ≥ 20 mm) or insignificant (i.e., < 20 mm). Documented by plain radiograph, CT, or venography.

Filter tilt – Angle of the longitudinal axis of the filter with respect to the longitudinal IVC axis. Tilt will be classified as significant (i.e., $\geq 16^\circ$ relative to the IVC longitudinal axis) or insignificant (i.e., $< 16^\circ$ relative to the IVC longitudinal axis). A filter is considered free of tilt if it appears centered in the IVC. Documented by plain radiograph or venography.

¹ Oh JC, Trerotola SO, Dagli M, Shlansky-Goldberg RD, Soulen MC, Itkin M, et al. Removal of retrievable inferior vena cava filters with computed tomography findings indicating tenting or penetration of the inferior vena cava wall. *J Vasc Interv Radiol.* 2011;22:70-74.

IVC thrombotic occlusion – Presence of an occluding thrombus in the IVC occurring after filter placement. Documented by ultrasound, CT, MR, venography, or autopsy. Methods of diagnosis should be noted, along with extent of thrombus. May be symptomatic or asymptomatic.

Major adverse events – Events of clinical perforation, clinical migration, clinical fracture, embolization of the filter or filter fragments to the heart or lungs, IVC thrombotic occlusion, new symptomatic DVT while a filter is indwelling, access site complications with clinical sequelae, and procedure-/device-related death.

Premature release of filter – The filter is released from the deployment system before the physician intended.

Procedure-/device-related death – Death directly attributable to the filter or filter placement or retrieval procedure itself, documented by clinical findings, imaging, or autopsy, or as adjudicated by a Clinical Events Committee.

Pulmonary embolism (PE) – Emboli to lungs via the pulmonary artery, which can arise from deep venous thrombosis in the lower extremities or pelvis. Documented using pulmonary arteriography, cross-sectional imaging, or significant change in ventilation/perfusion lung scan, or at autopsy. PE will be categorized by type.²

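### After filter retrieval, Section 6.3.2 counts only procedure-related deaths against primary safety, while Section 8.1.2 and Appendix C also count device-related deaths

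*Combined protocol and SAP*

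**What the plan says.** Section 6.3.2 and Section 8.1.2 give the same list of MAEs. In Section 8.1.2 it ends: "new symptomatic DVT while a filter is indwelling, access site complications with clinical sequelae, and procedure-/device-related death". DVT carries a limit to the time the filter is in place; death carries none.

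Appendix C repeats the list and defines the death component as "Death directly attributable to the filter or filter placement or retrieval procedure itself". It sets no time limit either. Several kinds of evidence may establish the attribution, and a committee ruling is one of them: "or as adjudicated by a Clinical Events Committee".

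Section 6.3.2 then adds a rule for the month after retrieval: "only the events of access site complications with clinical sequelae and procedure-related death will count against the primary safety endpoint". It describes the remaining events, which go to secondary reporting, as potentially new DVT without symptoms. Section 8.1.2, which defines the hypothesis test, does not repeat or refer to this rule.

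Section 12.1 has the Clinical Events Committee judge whether clinical events came from another condition or "were procedure-related, technique-related, and/or device-related". The term technique-related is not defined.

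Section 6.3.3 lists death and "Adverse events occurring after filter retrieval" as secondary measures.

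**The concern.** The most serious component of the primary safety endpoint has two counting rules for the same month. A patient whose filter is removed and who then dies of a cause attributed to the filter fails primary safety under Section 8.1.2 and Appendix C. Under the post-retrieval sentence of Section 6.3.2 the same patient does not fail.

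The month is not a corner of the study. Section 8.3 expects 60% of Celect filters to be retrieved before 12 months, so about 0.60 × 320 = 192 patients would enter it within the endpoint window.

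The discrepancy runs in one direction: following Section 6.3.2 as written can only raise the reported freedom from MAE. If the question arises over an actual death, it will have to be settled after the outcome is known.

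**Working it through.** **1. The passages side by side, for a death in the post-retrieval month with no earlier MAE**

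| Death attributed to | 6.3.2 post-retrieval rule | 8.1.2 list | Appendix C definition |
|---|---|---|---|
| Retrieval or placement procedure | counts | counts | counts |
| Filter only | does not count | counts | counts |
| Neither | does not count | does not count | does not count |

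Only the second row conflicts.

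**2. The plan's own safety figure**

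Inputs from Section 8.3: goal 80%, expected rate 92.2%, one-sided exact binomial test at 0.025, power 0.9. The smallest n that meets both conditions is 88, with success at 78 or more event-free patients (at most 10 failures). The exact type I error is P(F ≤ 10 | n = 88, p = 0.20) = 0.0238 and the power is 0.919. The stated 88 is reproduced. Allowing for 72% attrition, 320 × 0.28 = 89.6, which agrees with the enrolment target.

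**3. Effect of one uncounted death on the planned estimate**

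The planned test in Section 8.1.2 is Z = (Ŝ − 0.8)/SE with Ŝ from Kaplan-Meier. One event at time t multiplies Ŝ by 1 − 1/n(t), where n(t) is the number at risk, so the drop is about Ŝ/n(t). I take Ŝ = 0.922 and assume that n(t) lies between about 90 (the 28% left after attrition) and 320, with retrieved patients still in the risk set during that month:

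- n(t) = 320: 0.922/320 = 0.29 percentage points
- n(t) = 90: 0.922/90 = 1.02 percentage points

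The planned headroom is 92.2 − 80 = 12.2 points.

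**4. Binomial illustration only**

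If k true failures certainly occur and go uncounted, the rule behaves as if k more failures were allowed. At a true failure rate of 20%:

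| Evaluable patients | Failures allowed | None uncounted | One uncounted | Two uncounted |
|---|---|---|---|---|
| 88 | 10 | 2.4% | 4.6% | 8.3% |
| 320 | 49 | 1.9% | 2.7% | 3.8% |

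Neither row is the trial's decision rule. The 88 row fits least well: 88 is what remains after attrition that includes the 60% with retrieved filters, and the deaths at issue occur in exactly those patients.

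**The case against.** **The restriction may be deliberate.** Section 6.3.2 can be read as a general list followed by a specific rule, and Section 8.1.2 omits the rule for every component, not only death. The effectiveness endpoint has a parallel rule: PE after retrieval does not count. This is a fair reading. But the MAE list limits DVT by time and leaves death unlimited, and the description of the excluded events as DVT without symptoms does not fit a device-related death. Even if the restriction is intended, Section 8.1.2 and Appendix C would have to state it.

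**Few deaths fall in the gap.** This stands. Caval injury caused at retrieval is procedure-related and counts. Clinical perforation, clinical fracture or embolization while the filter is in place is already an MAE. Where a fragment is left behind, the retrieval does not meet the Appendix C definition of technical success; Section 7.8 keeps patients with an unsuccessful attempt on the post-placement schedule, so the restriction would arguably not apply. What is left is a death caused by the filter alone, after complete retrieval, with no earlier MAE. It would still appear in the secondary measures, though that does not correct the hypothesis test.

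**A reader might go further and infer that technique-related deaths also drop out.** The documents do not support this. Appendix C covers death from the placement or retrieval procedure, which ordinarily takes in operator handling. The and/or in Section 12.1 lets the committee assign more than one category, and committee adjudication is only one of the listed ways to document the death. What is missing is a written mapping for a death coded technique-related alone.

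**Conclusion.** The inconsistency is real and limited to device-related deaths in the month after retrieval. It concerns the definition of the primary safety endpoint, and the omission can only favour the device. Its expected effect on the Kaplan-Meier Z-test is small: roughly 0.3 to 1.0 points per death, under the risk-set assumption above, against 12.2 points of planned headroom. The documents give no rate for such deaths, so no expected number can be stated.

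Two stronger readings should be avoided. The rise in false-pass rate from 2.4% to 4.6% or 8.3% assumes that one or two such deaths certainly occur, and it uses a pass mark that the trial does not apply. The mortality in Section 4.0 (43 of 724 patients across the sponsor's studies, 26 of 129 in the Celect study) would scale to about 19 to 65 deaths among 320 patients. Those are deaths from all causes; they show how many may need adjudication, not how many would fall in this gap.

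Sample size and type I error allocation need no change.

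**What to change.** In the post-retrieval rule of Section 6.3.2, replace procedure-related death with procedure-/device-related death. State the same post-retrieval counting rule in Section 8.1.2, so that the endpoint and the hypothesis test use one definition.

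As a clarification only, add a line to Appendix C that a death coded technique-related by the Clinical Events Committee counts as procedure-related.

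The cost is wording in three places and a matching line on the adjudication form, best settled before any post-retrieval death is adjudicated. The downside for the sponsor is that the safety rate could be slightly less favourable.

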12.2 Adverse Event Reporting

Adverse events are to be reported to the data coordinating center using the appropriate CRF. In cases of serious adverse events or adverse device effects (i.e., adverse event with relation to the study device), completed forms should be submitted to the data coordinating center as soon as possible upon knowledge of the event.

The data coordinating center will review the information submitted for possible reporting to the sponsor. The sponsor shall, if required according to applicable regulations, report the event to the appropriate regulatory authority. The principal investigator or designee will notify his/her IRB/EC/REB of applicable events according to institutional guidelines. Investigators and clinical sites will be notified of applicable events by the sponsor, as appropriate.

13.0 Early Termination or Suspension of the Study

Any decision to suspend enrollment or terminate the study, either completely or at one or more sites, will be made by the sponsor and, if appropriate, the local IRB/EC/REB. If a decision is made to terminate the study, all patients will be followed according to institutional standard of care.

14.0 Ethical Considerations

This clinical study will be conducted in accordance with the ethical principles that have their origin in the Declaration of Helsinki and in accordance with global regulations including ISO 14155, ICH GCP, and 21 CFR 812.

The investigator is responsible for obtaining approval of this clinical study from the relevant IRB/EC/REB at his/her associated institution. The study will not begin until a favorable opinion of the IRB/EC/REB has been obtained. The investigator is responsible for complying with requirements imposed by their IRB/EC/REB and/or regulatory authority. Furthermore, the investigator will ensure that local regulations concerning data protection are followed.

